### **13.7 Clinical Trial Insurance**

Astellas has insurance coverage for medicine-induced injury and other liabilities incurred during clinical trials with its compounds.

### **13.8 Trial Report and Publications**

The trial will be documented in a final report, which will contain appropriate statistical analysis and medical overview. No individual site or investigator may publish or present any results from the trial until a joint, multi-center publication of the trial results is made by Sponsor in conjunction with various participating investigators and appropriate sites contributing data and comments. Subsequently, individual investigators may request to publish or present results from the trial; however, approval will be at the sole discretion of the Sponsor. Should the foregoing language be in conflict with the language addressing publication in the clinical trial agreement, the language in the clinical trial agreement will prevail.

## **14. MONITORING**

The investigator will permit representatives of Astellas to review all CRFs, trial documentation, and subject medical records at regular intervals throughout the trial. These monitoring visits are for the purpose of verifying protocol compliance, subject safety, and the adequacy of data collected.

## **17. APPENDICES**

### **17.1 Method for Evaluating Anterior Chamber Inflammatory Activity**

#### **17.1.1 Examination**

1. The pupils will be maximally dilated.
2. A slit-lamp biomicroscope will be used with a one by two mm^2 beam at an angle of 30-45°. The number of cells within this wedge will be counted.
3. The grade of anterior chamber inflammatory activity is determined.

#### **17.1.2 Standardized Description of Anterior Chamber Activity**

Anterior chamber activity will be graded on a scale of 0, trace, 1+, 2+, 3+, and 4+.

The grading is as follows:

0	None
Trace	< 5 cells in wedge
1+	5 - 10 cells in wedge
2+	11 - 20 cells in wedge
3+	21 - 50 cells in wedge
4+	> 50 cells in wedge

## **17.2 Method for Evaluating Vitreous Inflammatory Activity**

All subjects will have the standard fundus examination followed by evaluation for inflammatory activity in the vitreous.

### **17.2.1 Marking**

The clarity of the optic nerve head, retinal vessels, and the nerve fiber layer are used as landmarks for the marking criteria.

### **17.2.2 Examination**

1. The pupils will be maximally dilated.
2. An indirect ophthalmoscope and a 20+ diopter aspheric lens will be used as the standard.
3. Standard fundus examination is performed with the last view being over the disc and surrounding retina.
4. Inflammatory activity is evaluated by the examiner by determining which standardized description most closely resembles the vitreal haze seen through the indirect ophthalmoscope.

### **17.2.3 Standardized Description of Vitreous Inflammation**

Vitreous activity will be graded on a scale of 0, 1+, 2+, 3+, and 4+.

The grading is as follows:

0	No evident vitreal haze at all.
1+	Minimal haze. Optic nerve head and retinal vessels are both clearly defined.
2+	Retinal vessels are visible, but not clearly defined.
3+	Optic nerve head is visible but the borders are blurry, and cannot see vessels.
4+	Optic nerve head is obscured.

## **17.3 Procedures for Refraction and Vision Testing**

Refraction and visual acuity measurements will be performed for all subjects by a certified vision examiner. Another examiner should also be certified to serve as a back-up should the primary examiner be absent. The name and certification number of the vision examiner should be documented in the subject's source document at each visit. Visual acuity examiners are "masked" to previous visual acuity testing results. Therefore, visual acuity examiners should not have access to the subject's chart or previous visual acuity testing results. The previous refraction should be made available.

### **17.3.1 Refraction**

Refraction should be conducted prior to visual acuity testing to obtain best-corrected vision.

### **17.3.2 Equipment**

Refraction equipment required includes:

1. Retroilluminated light box and Charts R, 1 and 2 from Ferris-Bailey ETDRS distance visual acuity chart set
2. Trial lens frames
3. Trial lens set with plus or minus cylinder lenses
4. Jackson cross-cylinders of 0.25, 0.5, and 1.00 diopters
5. Pinhole occluder
6. Tissues or eye pads and tape
7. A 1 meter rigid measuring stick

### **17.3.3 Beginning Approximate Refraction**

At the Screening visit, the subject's beginning refraction is determined by one of the following methods:

- a) If the subject's visual acuity is 20/100 or better and the subject does not require glasses for distance vision, then the beginning approximate refraction should be no lens correction or plano.
- b) If the subject's visual acuity is 20/100 or better and the subject requires glasses for distance viewing, the glasses should be measured using a lensometer, and these measurements are used for the beginning refraction.
- c) If the subject's visual acuity is less than 20/100 with or without correction, then retinoscopy or autorefractometry should be performed.
- d) If the subject wears contact lenses for refraction, a notation should be made that the refraction was over contact lenses. It is suggested that the subject wear the contact lenses for future examinations. If the subject is not a regular contact lens wearer

and wore the lenses in by mistake, they should be removed and you should wait at least 30 minutes before beginning the refraction. The subject should be reminded not to wear contact lenses at subsequent visits.

Refractions are performed with either plus or minus cylinder power. Whichever cylinder type is used at screening (minus or plus) must be used for all subsequent visits. Best correction will be recorded on an examination form for each subject to be included in the source document. At each follow-up visit, the results of the protocol refraction from the previous visit are used as the beginning approximate refraction. If the previous refraction is not available for whatever reason, the procedure described immediately above should be used. *Note: The distance prescription worn in glasses should be used only as the starting point for the Screening Visit. All subsequent visits should use the previous refraction as the starting point.*

The charts used for measuring distance visual acuity must NOT be used for refraction. Refraction for each eye should be performed at 4 meters unless the subject's visual acuity measured at 4 meters on the refraction chart (Chart R) is worse than 20/160. If visual acuity is worse than 20/160 the eye is refracted at 1.0 meter. If during the refraction process at one meter, the subject is reading letters on the eighth line or lower, the refraction should continue at 4 meters. Whenever a subject cannot read any letters on the top line of Chart R at 1.0 meter the vision should be checked with a pinhole to see whether reduced vision is due, at least in part, to a larger refractive error. If there is no improvement with the pinhole, then the eye is exempt from refraction.

Subjective refraction as described below should be performed for corrected aphakic subjects, including those with intraocular lenses. For uncorrected aphakic subjects, a +10.00 diopter sphere should be added to the trial frame as the beginning approximate refraction.

### 17.3.4 Subjective Refraction

Subjective refraction allows one to determine the best correction for a subject to perform the visual acuity tests at specified distances. The “push plus” approach is used in this trial. Add minus diopter spherical corrections only when the subject is able to read at least one more letter on a line or a letter on a smaller line.

### 17.3.5 Procedure

1. Measure the distance vision of each eye using Chart R while occluding the fellow eye (FE). Subjects should be reminded to blink and encouraged to use eccentric fixation, or their side vision, when necessary.
2. All vision testing must be done at 4 meters or 1 meter from Chart R, depending upon the visual acuity determined at 4 meters. Distance for 4 meters is 13 feet and 1.5 inches or 157.5 inches. The one meter distance is 39 and 3/8 inches.
3. All subjects should be seated for testing. A rigid measuring device should be used to measure the distance from the subject to the chart at each visit if testing is done at 1 meter. The distance is measured from the outer canthus to the center of the second letter (left eye) or fourth letter (right eye) of the third line of the chart. If testing is done at 4 meters, **clear and permanent** floor markings should be used to mark the distance for consistency.
4. Place and adjust the trial frame on the subject’s face so that the lens cells are parallel to the anterior plane of the orbits and centered in front of the pupils. Adjust the lens cells for the proper distance from the cornea.
5. Occlude the left eye by lightly patching with an eye pad or tissue and tape.
  - a) Place the spherical lens correction in the compartment closest to the eye.
  - b) The cylindrical lens correction, if present, is placed in the compartment in front of the spherical correction. Adjust the axis.
6. **Spherical Correction:** To determine the highest plus or least minus sphere, refract the right eye. **The following refraction steps are recommended for visual acuities of 20/10 to 20/80 with the beginning approximate refraction. For visual acuities less than 20/80, refer to the refraction table for the appropriate sphere and cylinder powers and testing distance (See 17.3.10) and follow a similar procedure.** *Note: Whenever visual acuity is improved to a higher range by improved correction, refraction should be performed with the smaller sphere and cylinder powers given for the better visual acuity level (See table at end of this appendix).*
  - a) Hold a +0.50 sphere in front of the subject’s right eye. The subject should be looking at the smallest legible line on the visual acuity chart. In these exact words, ask the subject, “Is this better, worse, or no change?”

- b) If the subject responds that the vision is worse or blurred, remove the +0.50 sphere from in front of the trial frame, record the visual acuity to the nearest letter, and go to Step 6d.
  - c) If the subject responds better or no change, remove the +0.50 sphere from in front of the trial frame and replace the spherical lens in the trial frame with a spherical lens that is one-half diopter more positive. Continue this procedure by returning to Step 6a and repeating this process until a +0.50 makes the vision worse or blurred and then go to Step 6d.
  - d) Hold a -0.50 sphere in front of the subject's right eye. In these exact words, ask the subject, "Is this better, worse or no change?" If the subject replies "worse" or "no change", go to Step 6f. If they reply "better" go to step 6e.
  - e) Hold the -0.50 sphere in front of the eye. If the subject responds that the vision is better, ask the subject to read the visual acuity chart. Whenever the visual acuity is improved, even by one letter, you may increase the minus by 0.50 (or decrease the plus) and repeat Step 6d. Whenever visual acuity is not improved, go to Step 6f.
  - f) Remove the -0.50 sphere from in front of the eye and hold a +0.50 sphere in front of the right eye. In these exact words, ask the subject, "Is this better, worse, or no change?" If the subject responds that vision is better or unchanged, then return to Step 6c. Otherwise, go to Step 7. Spherical testing should always end with a plus lens.
7. **Cylinder Axis**: To determine and refine the cylinder axis for PLUS cylinder, proceed as follows (*If negative cylinders are used, the appropriate technique using minus cylinders must be employed and minus cylinder must be used throughout the trial.*):
- a) Have the subject look at a line, which is either one or two lines larger than the smallest line the subject is able to read. Ask the subject to focus on a rounded letter such as "C", "D", or "O". The subject should focus on this same letter throughout this procedure.
  - b) If a cylinder is present in the beginning approximate refraction, then go to Step 7c. Otherwise, follow one of the options listed below to determine the appropriate cylindrical correction.

**Option 1:**

Place a +0.50 diopter cross-cylinder with the positive axis (white) first at 90°, then at 180°, then 45°, and 135°. If the subject says that vision is improved at any one of these axis positions, place a +0.50 cylindrical lens in the trial frame at the preferred axis and go to Step 7c. If none of the positions are preferred, then proceed to Step 9.

**Option 2 (preferred):**

Place a +0.50 diopter cross-cylinder with the positive axis (white) first at 90°, then compare this to no cylinder; repeat this procedure for 180°, then 45°, and 135° always comparing to no cylinder after each axis position. If the subject says that vision is improved at any one of the four axis positions, place a +0.50 cylindrical lens in the trial frame at the preferred axis. If the subject prefers no cylinder at all four axis positions, then go to Step 9.

- c) Place the +0.25 diopter cross-cylinder (for visual acuity 20/10-20/80) first with the positive axis 45° to the right of the preferred cylinder axis (as determined above), and second with the positive axis 45° to the left of the preferred cylinder axis. Ask the subject, “Which do you like better, position one or position two?” Also, tell the subject that both positions may blur their vision. The subject must choose the least blurred position, either one or two. “Neither” is allowed only if both positions are equally blurred or equally good.
- d) If “neither” position is better and this was the first test of axis position, move the axis of the cylinder in the trial frame 15° to the right or left and return to Step 7c. Otherwise, proceed to Step 7e.
- e) When one position is preferred over another, move the cylinder to the preferred positive axis position in the step sizes noted below and return to Step 7c. If no single position is better than another than go to Step 8.

**CYLINDER REFINEMENT - AXIS STEP SIZES**

Cylinder Power	Axis Step Sizes
< 1.00D	15°
1.00 - < 2.00D	10°
2.00 - < 3.00D	5°
3.00 - < 5.00D	3°
5.0 - < 8.00D	2°

8. **Cylinder Power:** Cylinder power is refined by following the steps:

- a) Ask the subject to look at the smallest line that can be read on the visual acuity chart.
- b) Test the cylinder power by placing the 0.25 diopter cross-cylinder (for vision of 20/10-20/80) first with the positive axis and second with the negative axis coincident with the cylinder axis. Ask the subject, "Which is better, position one or position two?" Do not give the subject the choice of neither.
- c) If the subject prefers the negative (red) axis coincident with the cylinder axis, the total power of the correcting plus cylinder is reduced by 0.25 diopter. Repeat the process until the subject cannot choose one of the cross cylinder positions over the other. If the subject indicates a change that would introduce negative cylinder power, remove all cylinder power and continue testing for positive cylinder power at an axis 90° away from the previous axis. Otherwise go to Step 8d.
- d) If the subject prefers the positive (white) axis coincident with the cylinder axis, increase the power of the cylinder by 0.25 diopters and return to Step 8b. Otherwise proceed to Step 8e.
- e) When the subject feels that both positions are equally bad or good, and the cylinder power in the trial frame has changed by more than 0.50 diopter, return to Step 7c and re-adjust the axis if necessary. Otherwise, proceed to Step 9.

*Note: If the cylinder is changed by more than 0.50 diopter, the spherical equivalent should be maintained. (For each 0.50 **plus** CX increase, add -0.25 to the sphere, for each 0.50 **minus** CX increase, add +0.25 to the sphere).*

9. **Spherical Correction Refinement:** Recheck the power of the sphere by adding +0.25 and -0.25 spheres and changing the spherical power by 0.25 diopter increments of the appropriate sign until the subject cannot detect any improvement

in vision. As a reminder, spherical testing should always begin and end with a plus lens.

10. Record the lens corrections obtained by subjective refraction for the right eye on the examination form in the section for visual acuity measurements as the corrections obtained by protocol refraction for the right eye. If the corrective power was changed by more than 2 diopters from the starting refraction, confirm that the subject can read at least as well as the beginning approximate refraction. If not, then begin again at Step 1 and repeat the process.
11. Repeat the entire process (Steps 1-10) for the left eye and record the result on the examination form.

### **17.3.6 Visual Acuity Testing**

Best-corrected visual acuity is measured at all trial visits using standard charts, lighting, and procedures. Best correction is determined by careful refraction at that visit according to the standard protocol for Refraction as described in the previous section.

### **17.3.7 Visual Acuity Charts**

Chart 1 is used for testing the visual acuity of the right eye; Chart 2 for testing the left eye; and Chart R for testing refraction only. Subjects should not be allowed to see any of the charts before the examination.

### **17.3.8 Visual Acuity Lane and Visual Acuity Box**

A distance of **4 meters** is required between the subject's eyes and the visual acuity chart. With the box light off, not more than 15 foot-candles of light (161.4 Lux) should fall on the center of the chart. To measure the amount of light, the room is set up for visual acuity testing, but with the box light off. The light meter is placed at the fourth line from the top of the chart, with its back against the chart and the reading is taken. If more than one lane is available for testing visual acuity, the visual acuity of an individual subject should be measured in the same lane at each visit, if possible. If different lanes are used to test visual acuity, they must each meet the same standards.

Retroilluminated ETDRS charts are used in this trial. The illuminator box will be either wall-mounted or mounted on a stand manufactured by the Lighthouse Low Vision Services. The light box should be mounted at a height such that top of third row letter is  $49 \pm 2$  inches from floor.

The visual acuity light box is equipped with two General Electric Cool Daylight 20-watt fluorescent tubes and a ballast which partially covers the tubes. Because the illumination of fluorescent tubes diminishes by 5 percent during the first 100 hours and

by another 5 percent during the next 2000 hours, new tubes should be kept on for 4 days (96 hours) continuously, and should be replaced once a year.

A sticker should be placed on the back of the light box, indicating the date on which the present tubes were installed. A spare set of burned in bulbs should be available on site.

Each tube is partly covered by a 14-inch fenestrated sleeve, which is open in the back. This serves as a baffle to reduce illumination. Each sleeve should be centered on the tube with the opening towards the back.

### **17.3.9 Corrected Visual Acuity Measures**

- As a reminder, Charts 1, 2, and R are used for testing the right eye, left eye, and refraction, respectively. Subjects should not see the charts until the test begins.
- All eyes must be tested at 4 meters first, even if the refraction was performed at 1 meter.
- The subject should be seated comfortably directly in front of the chart so that the eyes remain at the 4 meter distance. Testing always begins with the right eye. Occlude the subject's left eye. A folded tissue or eye pad lightly taped over the eye behind the trial frame serves as an effective occluder that allows eccentric fixation without inadvertent use of the covered eye. After testing the right eye, occlusion of the right eye should be done BEFORE Chart 2 is put up for testing the left eye.
- The lens correction from the subjective refraction should be in the trial frame worn by the subject.
- The subject is asked to read the letters slowly, approximately one letter per second. The subject should be told that only one chance is given to read each letter on the chart. If the subject is unsure about the identity of the letter, then the subject should be encouraged to guess.
- The subject should begin by reading the top line of the chart and continue reading every letter on each smaller line, from left to right on each line. The examiner circles every correct letter read and totals each line and the whole column (0 if no letters are correct) on the data collection form. An X is put through letters read incorrectly. Letters, for which no guess was attempted, are not circled. When a subject reaches a level where he/she cannot guess, the examiner may stop the test provided that the subject has made errors on

previous guesses, which is a clear indication that the best visual acuity has been obtained.

- When a subject cannot read at least 20 letters on the chart at 4.0 meters, the subject is tested at 1.0 meter. The distance from the subject to the chart should be measured again using the rigid one meter stick. The distance is measured from the outer canthus to the center of the fourth letter (right eye) or the second letter (left eye) of the third line of the chart. The spherical correction in the trial frame should be changed by adding +0.75 to correct for the closer test distance. The subject may fixate eccentrically or turn or shake his/her head to improve visual acuity. If this is done, the examiner must ensure that the FE remains occluded both centrally and peripherally and that the subject does not move forward in the chair. Particular care should be taken to make sure the subject does not move forward when testing at 1 meter. The subject should be reminded to blink.
- The examiner should not tell the subject if a letter was identified correctly. The subject may be encouraged by neutral comments, such as “good”, “next”, and “OK”.
- The examiner should not stand close to the chart during testing. Attention should be focused on the subject and the data collection form. If the subject has difficulty locating the next line to read, the examiner may go up to the chart and point to the next line to be read, but then must move away from the chart.
- When it is possible to measure the visual acuity of the eye at 4.0 meters (i.e. 20 or more letters read at 4 meters), the visual acuity score for that eye is recorded as the number of letters correct plus 30. The subject gets credit for the 30 1M letters even though they did not have to read them. Otherwise, the visual acuity score is the number of letters read correctly at 1.0 meter plus the number, if any, read at 4M. If no letters are read correctly at either 4.0 meters or 1 meter, then the visual acuity score is recorded as 0.

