### 17.3.10 Refraction Sequence Chart

Refraction Protocol Summary							
Vision with Best Correction (Refraction Distance)	Sphere		Cylinder			Sphere Refinement	
	Power (a)	Increment	Axis (b)	Power (c)	Increment	Power (d)	Increment
20/10 - 20/80 (4 meters)	+ .50	+ .50	.25	.25	+ .25	+ .25	+ .25
	- .50	- .50	JCC	JCC	- .25	- .25	- .25
20/100 - 20/160 (4 meters)	+1.00	+1.00	.50	.50	+ .50	+ .50	+ .50
	-1.00	-1.00	JCC	JCC	- .50	- .50	- .50
20/200 - 20/400 (1 meter)	+2.00	+2.00	1.00	1.00	+1.00	+1.00	+1.00
	-2.00	-2.00	JCC	JCC	-1.00	-1.00	-1.00
<20/400 (1.0 meters)	+2.00	+2.00	No cylinder test			No refinement	
	-2.00	-2.00					

Sequence of Refraction: (a) - (d)

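### Eyes whose final refraction is at 1 m are tested with a nominal 0.75 D of excess plus at both 4 m and 1 m, and this enters BCVA change when the refraction distance changes during follow-up

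*Protocol*

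**What the plan says.** **Which eyes are refracted at 1 m.** Protocol Section 17.3.3: "If visual acuity is worse than 20/160 the eye is refracted at 1.0 meter". The chart in Section 17.3.10 agrees, giving 1 m for 20/200 to 20/400 and for anything worse. There is a way back: if, during the 1 m refraction, "the subject is reading letters on the eighth line or lower, the refraction should continue at 4 meters". Eyes that cannot read the top line at 1 m and gain nothing from a pinhole are not refracted at all.

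**What is carried forward.** Section 17.3.5, step 10: "Record the lens corrections obtained by subjective refraction for the right eye on the examination form"; step 11 repeats this for the left eye. Neither step converts the lens to a standard distance.

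**What is worn for the acuity test.** Section 17.3.9: "All eyes must be tested at 4 meters first, even if the refraction was performed at 1 meter". Of the lens it says: "The lens correction from the subjective refraction should be in the trial frame worn by the subject". Then: "When a subject cannot read at least 20 letters on the chart at 4.0 meters, the subject is tested at 1.0 meter", and for that move "The spherical correction in the trial frame should be changed by adding +0.75 to correct for the closer test distance". An eye below 20 letters at 4 m is scored on its 1 m letters plus any 4 m letters, so both tests count.

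**Where the score is used.** Change in BCVA at Month 18 is the second hypothesis in the fixed sequence (SAP Section 2.1). BCVA also defines time to persistent vision loss (SAP Section 4.5). Study eyes may enter at 20/200 (Protocol Section 8.2.2).

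**The concern.** Moving a chart from 4 m to 1 m calls for 0.75 D more plus. The protocol's increment is therefore correct when the starting lens was found at 4 m. An eye refracted at 1 m has that allowance in its lens already. Section 17.3.9 plainly foresees this eye, since it requires the 4 m test even after a 1 m refraction. Yet nothing in Section 17.3 takes 0.75 D out before the 4 m test or waives the addition at 1 m.

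The excess depends on the refraction distance. An eye that moves from 4 m to 1 m refraction during follow-up therefore gains it after baseline. Part of its measured letter loss would then come from the lens rule and not from the retina, in an endpoint that is tested confirmatorily and compared with loss thresholds of 10, 15 and 20 letters.

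**Working it through.** **Inputs.** Test distances of 4 m and 1 m and the increment of +0.75 D (Section 17.3.9); refraction distances (Sections 17.3.3 and 17.3.10). Required plus, relative to a distant target, is 1/distance in metres.

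**Step 1: the plan's own figure.** 1/1 − 1/4 = 1.00 − 0.25 = 0.75 D. This reproduces the protocol's increment exactly.

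**Step 2: excess plus as written** (lens in the frame minus lens needed).

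| Refracted at | 4 m test | 1 m test |
|---|---|---|
| 4 m | 0.25 − 0.25 = 0.00 D | (0.25 + 0.75) − 1.00 = 0.00 D |
| 1 m | 1.00 − 0.25 = +0.75 D | (1.00 + 0.75) − 1.00 = +0.75 D |

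**Step 3: which eyes.** Assume a chart with a 20/200 top line at 4 m and steps of 0.1 log unit. At 1 m the top line is then 20/800, and line 8 is 800/10^0.7 ≈ 160, that is, about 20/160. The eighth-line rule therefore returns to 4 m those eyes that prove to be near 20/160. The affected group is eyes whose final refraction stays at 1 m.

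With five letters per line, 20/160 is 10 letters at 4 m, 20/125 is 15 and 20/100 is 20. Eyes of about 20/125 to 20/160 are thus refracted at 4 m, fall below 20 letters and move to 1 m. For them the +0.75 D is right, so the step cannot simply be deleted.

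**Step 4: what reaches change from baseline** (nominal excess at Month 18 minus excess at baseline).

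| Baseline → Month 18 refraction | Difference in excess | Effect on measured change |
|---|---|---|
| 4 m → 4 m | 0.00 − 0.00 = 0.00 D | none |
| 1 m → 1 m | 0.75 − 0.75 = 0.00 D | largely cancels |
| 4 m → 1 m | 0.75 − 0.00 = +0.75 D | decline exaggerated |
| 1 m → 4 m | 0.00 − 0.75 = −0.75 D | gain exaggerated |

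In a progressive disease the third row should be commoner than the fourth, which is why the net tendency is towards exaggerated decline. Baseline BCVA for the study eye is the average of the last two pre-treatment values (SAP Section 4.1). An eye refracted at different distances at those two visits carries the offset in one of the two values.

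**Step 5: check of the remedy.** Take 0.75 D from the 1 m lens: 1.00 − 0.75 = 0.25. At 4 m, 0.25 − 0.25 = 0.00 D. At 1 m, (0.25 + 0.75) − 1.00 = 0.00 D.

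**The case against.** *Few eyes may be involved.* A reader might infer that every visit of every eye worse than 20/160 is affected. The eighth-line rule rules that out, and eyes near the 20/200 entry limit sit close to its trigger. This stands: the documents support only the narrower group, and they do not give its size.

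*The offset is smaller than the lens steps.* For 20/200 to 20/400, Section 17.3.10 uses sphere steps of 2.00 D with 1.00 D refinement, and below 20/400 there is no refinement. Follow-up refraction starts from the previous lens (Section 17.3.3). An eye newly refracted at 1 m may therefore end with none of the 0.75 D, or with more. This stands as a reason to call 0.75 D nominal and to expect individual errors to vary. Coarse steps do not remove a shift that is built into the target.

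*Accommodation.* An eye that accommodates during the 1 m refraction may accept less than the full 0.75 D. The procedure works against this, because it favours the highest acceptable plus and ends sphere testing on a plus lens (Sections 17.3.4 and 17.3.5). At the test itself accommodation cannot help, since it adds plus.

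*No false treatment effect.* A reader might infer bias between arms. The rule is the same in both, and examiners are masked to treatment and to earlier acuity results (Protocol Sections 11.4.1 and 17.3). If the arms truly differ in how often eyes change distance, the size of that difference can be distorted, but the rule does not create one. BCVA is also tested only after success on the OCT-based primary endpoint.

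*Practice may differ from the text.* Certified examiners may convert the lens as a matter of routine. The documents do not say, so this has to be established.

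**Conclusion.** The point holds for eyes whose final refraction is at 1 m. As written, Section 17.3.9 gives them a nominal 0.75 D of excess plus at both test distances, against none for eyes refracted at 4 m. It largely cancels for eyes refracted at 1 m throughout. It reaches change in BCVA and persistent vision loss through eyes whose refraction distance changes, where it mainly adds noise and tends to exaggerate decline. The primary endpoint is untouched.

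This assumes that examiners follow the text literally and that the 1 m refraction reaches its proper end-point. It is tempting to turn 0.75 D into a number of letters and set that against the 10-letter threshold. The documents give no letters per dioptre and no count of affected eyes, so no such figure can be defended and the effect could be small. The correction is still worth making, because the rule gives the wrong lens for a confirmatory endpoint and is easily put right.

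**What to change.** 1. Reconcile Sections 17.3.3, 17.3.5 (step 10) and 17.3.9 with one sentence. A refraction done at 1 m has 0.75 D sphere removed before the 4 m test, and the +0.75 D at 1 m is added only to a lens set for 4 m. Equivalently, a 1 m refraction is used unchanged for the 1 m test.
2. Record the refraction distance with each BCVA.
3. For data already collected, establish before unmasking what examiners actually did and flag the visits refracted at 1 m. Add to the SAP a BCVA sensitivity analysis directed at eyes whose refraction distance changed.

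Step 3 matters because the SAP's Appendix 1 describes allocation in the past tense and Amendment C is dated 21 Mar 2025. If follow-up is still running, a new lens rule applied only to later visits would itself create a shift from baseline in affected eyes.

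The cost is one sentence, an examiner memo, one source field, a masked look at refraction records and one extra analysis. No visit or procedure is added.
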